4.4.2 Hematologic (Blood/Bone Marrow) Toxicity

Dose delays or dose modifications are not required for hematologic toxicities unless the disease assessment shows bone marrow hypoplasia (< 5% cellularity). It is assumed that any cytopenia at diagnosis is due to resistant AML.

Management of neutropenia, neutropenic fever, thrombocytopenia, anemia, or bleeding should follow standard guidelines within the institution.

In the absence of medical indications (surgery, bleeding) platelet transfusions should be given to maintain counts > 10,000/ μ L .

Erythropoietin, G-CSF, or GM-CSF may not be used during protocol treatment.

5. PRIOR AND CONCOMITANT MEDICATIONS

5.1 Prior Medications and Therapy

Relevant medical history should be obtained at screening and include prior medications and treatment history for AML, as well as prior cytotoxic therapy, chemotherapy, or radiation therapy for conditions other than AML. All medications taken within 2 weeks prior to screening, regardless of indication, should be recorded.

5.2 Concomitant Medications and Therapy

Any therapy or medication (except study drugs), administered from screening until 28 days after the last dose of either study drug, is considered a concomitant therapy or medication. However, if another course of anti-cancer therapy is initiated prior to the 28-day follow-up period visit, a record of concomitant medications will no longer be performed. If the use of any concomitant treatments (medications or procedures) becomes necessary, the treatment must be recorded, including the name of the drug or treatment, dose, route, date, indication for use, expected duration, and frequency of treatment. Assessment and documentation of concomitant medications will be done at each weekly visit.

Within 14 days of the first dose of ciprofloxacin and throughout this study, subjects may not receive any other chemotherapy or any investigational agent. The use of hydroxyurea is allowed only during the first 14 days of Cycle 1. Concomitant medications should be kept to a minimum on Days 1 – 12 of each cycle. Anti-emetics and other supportive medications such as antibiotics should be recorded on the CRF.

No other fluoroquinolone should be administered throughout the study unless mandated by resistant infection. Prophylactic levofloxacin is not allowed. If other fluoroquinolones are required, ciprofloxacin must be stopped. Otherwise, the administration of prophylactic antimicrobials is left to the discretion of the treating physician. On study Days 1 – 12 every effort should be made to give fluconazole at a dose of no more than 100 mg daily and to avoid voriconazole.

Subjects should receive appropriate treatment prior to, during and after study treatment as medically indicated to prevent tumor lysis syndrome.

Nausea and/or vomiting prophylaxis and control should be administered per institutional guidelines. Anti-emetics should be taken 15-30 minutes prior to each etoposide dose with dexamethasone 4-8 mg orally being favored. The anti-emetic chosen should be based on treatment- and subject-related factors, and prior history of control of nausea and/or vomiting. Medications that can prolong the QTc interval are relatively contraindicated on Days 1 – 12 of each cycle. A non-comprehensive list of these medications is listed in [Appendix C](#). Subjects taking one or more of these medications may participate in the clinical study providing that they meet QTc eligibility criteria.

Medications with expected/known drug interactions with ciprofloxacin or etoposide should be avoided, if possible. Dose adjustments and/or alternative medications should be made whenever possible. Each subject's medication list should be reviewed at each study visit for any potential drug interactions, and any medication adjustment decisions should be made by the treating provider.

Ciprofloxacin is a known inhibitor of human cytochrome P450 1A2. Ciprofloxacin may increase the toxicity of medications that are metabolized by this enzyme including theophylline, tizantidine, duloxetine, propranolol, and caffeine. Therapy with these agents should be closely monitored.

Etoposide is a major substrate of human cytochrome P450 3A4 and P-glycoprotein. Medications that are strong inhibitors of this enzyme/transporter should be avoided if possible, or dose adjustments made. All subjects should be counseled to avoid grapefruit or juices containing grapefruit while on treatment with ciprofloxacin and etoposide.

The following drugs are also excluded:

- filgrastim (G-CSF, Neupogen);
- sargramostim (GM-CSF, Leukine);
- peg-filgrastim (Neulasta);
- erythropoietin (EPO, Procrit);
- darbopoyetin (Aranesp);
- concomitant anti-cancer treatment(s);
- revlimid (lenalidomide);
- retinoids;

- interleukin-11;
- thalidomide;
- interferon;
- azacitidine (Vidaza);
- decitabine (Dacogen); and
- Other investigational drugs.

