	
I. Males with female partners of child-bearing potential must agree to use physician-approved contraceptive methods (e.g., abstinence, condoms, vasectomy) throughout the study and should avoid conceiving children for 6 months following the last dose of ciprofloxacin and/or etoposide.
 
J. Subjects must have provided written informed consent, and demonstrated the willingness and ability to comply with all study-related procedures.
 
Exclusion criteria - None of the following can apply:
 
A. History of allergic or significant adverse reaction (e.g., anaphylaxis, prolonged QTc, or severe tendonitis) to ciprofloxacin or etoposide.
 
B. Acute promyelocytic leukemia (APL) with t(15;17).
 
C. Prolonged baseline QTc, defined as QTc interval > 470 msec in women and > 450 msec in men, or > 480 msec for subjects with a bundle branch block.
 
D. Uncontrolled clinically significant infection. Subjects with fever (temperature $\geq 38.3^{\circ}\text{C}$) thought to be related to leukemia are eligible assuming that blood cultures are negative during the 7 days prior to Cycle 1 Day 1 and there is no clinical evidence of active infection (e.g., negative or stable radiographs and negative physical examination).
 
E. Ongoing, symptomatic Clostridium difficile infection. Subjects who are asymptomatic with negative stool for C. difficile may participate.
 
F. Pregnant and/or nursing.
 
G. History of Myasthenia Gravis.
 
H. Treatment with any anticancer therapy (standard or investigational) within 14 days prior to the first dose of ciprofloxacin or less than full recovery (\leq CTCAE Grade 1) from the clinically significant toxic effects of that treatment. The use of hydroxyurea is allowed only during the first 14 days of cycle 1.

Study Duration and Dates:
	
 • It is estimated that the subject recruitment period will be approximately 48 months. No subject will receive more than 2 cycles of therapy from Day 1 of Cycle 1. • Data regarding disease status and overall survival will be collected monthly until disease progression, death or until 3 years from the on-study date.

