1. BACKGROUND AND RATIONALE

1.1 Management of Resistant Acute Myeloid Leukemia (AML)

Patients with AML who fail induction chemotherapy (refractory) and those who relapse after optimal chemotherapy are seldom cured with salvage regimens (6). While allogeneic stem cell transplantation can cure 30-50% of patients with resistant AML who are transplanted in complete remission (CR), most patients are not candidates due to failure to achieve CR with salvage therapy or due to comorbid conditions or absence of a suitable donor.

Given that resistance to chemotherapy is the major cause of death for patients with AML, there is an urgent need for novel treatment regimens that are well tolerated and capable of overcoming disease resistance (7). Recent advances in molecular genetics have revealed that AML is characterized by a complex, sub-clonal architecture that evolves spontaneously and in response to treatment. Chemotherapy-resistant leukemia clones can quickly become dominant by “survival of the fittest” dynamics. In order to target minor, yet resistant clones, one strategy is to augment the effectiveness of current chemotherapeutic agents.

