2.2 Secondary

In subjects with resistant AML, to

- Determine the safety and feasibility of treatment with ciprofloxacin and etoposide;
- Measure the response duration, progression-free and overall survival (PFS and OS respectively);
- Estimate the incidence of Grade ≥ 3 adverse events following treatment with ciprofloxacin and etoposide at the MTD.

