6.4 Follow up/Survival

Subjects will have a follow-up visit for the evaluation of adverse events and concomitant medications 28 days (± 7 days) after the last study medication dose.

Follow-up evaluations will be performed for clinically significant abnormal physical examinations or abnormal laboratory findings, 12-lead ECGs, or vital signs, as deemed necessary by the treating physician.. All subjects who have adverse events, whether considered associated

with the use of the study drugs or not, must be monitored to determine the outcome. The clinical course of the adverse event will be followed according to accepted standards of medical practice, even after the end of the period of observation, until a satisfactory explanation is found or the Principal Investigator deems it medically justifiable to terminate follow-up.

All subjects will be followed monthly until: disease progression, death, or until 3 years from the on-study date.

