8.2 Period of Observation

For the purpose of this study, the period of observation for adverse events starts on the day the subject signs informed consent. For subjects who fail screening, the period of observation ends on the date of screening failure. Treated subjects, including those who were prematurely discontinued from the study, will be followed for any adverse events that occur during the study from the time the subject signs the informed consent form until 28 days (± 7 days) following the last dose of study treatment (i.e., the Follow-up Visit). However, if another course of anti-cancer therapy is initiated prior to the 28-day follow-up period visit, collection of adverse events will no longer be performed, with the exception of events that may be possibly, probably, or definitely related to the investigational agent or are clinically significant.

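### Transplant and other later anti-leukemia therapy are neither specified for collection after the 28-day window nor handled in the analysis, so response duration, and PFS when such therapy precedes progression, would mix its effect with the regimen's

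*Combined protocol and SAP*

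**What the plan says.** Section 2.2 sets the secondary objective: "Measure the response duration, progression-free and overall survival (PFS and OS respectively"). The Synopsis words it as duration of complete response, of PFS and of OS.

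Treatment is capped at two 28-day cycles (Sections 3.1 and 3.4). Section 6.4 then provides: "All subjects will be followed monthly until: disease progression, death, or until 3 years from the on-study date". The Synopsis (Study Duration and Dates) names the data: "Data regarding disease status and overall survival will be collected monthly until disease progression, death or until 3 years from the on-study date". In Table 1 the long-term follow-up column has a mark only for survival assessment; the medication history row is blank there.

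Section 5.2 defines the recording window. Any therapy "administered from screening until 28 days after the last dose of either study drug, is considered a concomitant therapy or medication". It closes earlier in one case: "if another course of anti-cancer therapy is initiated prior to the 28-day follow-up period visit, a record of concomitant medications will no longer be performed". Section 8.2 has a parallel rule for safety, under which "collection of adverse events will no longer be performed" once new anti-cancer therapy starts, apart from events that may be related or are clinically significant.

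Section 11.3.2 summarizes all efficacy endpoints by frequency distributions, with 95% confidence intervals for proportions. It gives no time-to-event method, no censoring rule and nothing on subsequent therapy.

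On transplant, Section 1.1 says that "allogeneic stem cell transplantation can cure 30-50% of patients with resistant AML who are transplanted in complete remission (CR").

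**The concern.** Transplant in remission happens before relapse, so it falls inside response duration and PFS. By the protocol's own account it can be curative, and responders are the subjects for whom it becomes possible. Subjects with stable disease or partial response after Cycle 2 also leave treatment without having progressed; any therapy they start before progression can lengthen their PFS.

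Response duration and PFS would be read as evidence of whether remissions on ciprofloxacin and etoposide last. If the start of later therapy is not recorded, the reader cannot tell how much of that time belongs to the regimen. With few responders, one or two transplanted subjects could dominate the tail of the curve.

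**Working it through.** **The plan's own figures.** None is stated for response duration, PFS or OS. The only powered figure is the Simon minimax design in Section 11.1: stop at 2 or fewer responses in 14, reject at 8 or more in 24, 20% against 40%. The probability of rejection is the sum over x = 3 to 14 of P(X1 = x; 14, p) × P(X2 ≥ 8 − x; 10, p). It is 0.0874 at p = 0.20 (limit 0.10) and 0.8024 at p = 0.40 (target 0.80). Enrolment is 24 / (1 − 0.20) = 30. These figures reproduce. CR is assessed at the end of a treatment cycle, so recording later therapy changes none of them.

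**Recording window against follow-up.** The last ciprofloxacin dose is on Day 10 of a cycle. Without delays the window closes on study day 10 + 28 = 38 after one cycle, or 28 + 10 + 28 = 66 after two. Follow-up can run to 3 years, about 1,095 days, so the window covers at most 66 / 1,095 = 6% of it.

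**Expected responders.** In 24 evaluable subjects: 24 × 0.40 = 9.6 at the alternative and 24 × 0.20 = 4.8 at the null. If 10-50% of them were transplanted (an assumption), that is 1.0 to 4.8 subjects, or 0.5 to 2.4.

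**Illustration for response duration.** Assumptions, none taken from the documents unless stated:
- remission without transplant is exponential with median m = 4 or 6 months, so S(t) = 2^(−t/m);
- a share p of responders is assigned to transplant at 2 months and receives it if still in remission;
- a share c = 40% of those transplanted is cured (the middle of the 30-50% in Section 1.1); the others relapse at the unchanged rate.

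Remission at 12 months is then S(2) × [(1 − p)S(10) + p(c + (1 − c)S(10))]. Since S(2)S(10) = S(12), this equals S(12) + p × c × [S(2) − S(12)].

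- m = 4: S(2) = 0.7071, S(12) = 0.1250, difference 0.5821.
- m = 6: S(2) = 0.7937, S(12) = 0.2500, difference 0.5437.

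| Median | No transplant | p = 10% | p = 30% | p = 50% |
|---|---|---|---|---|
| 4 months | 12.5% | 14.8% (+2.3) | 19.5% (+7.0) | 24.1% (+11.6) |
| 6 months | 25.0% | 27.2% (+2.2) | 31.5% (+6.5) | 35.9% (+10.9) |

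For example, with m = 4 and p = 30%: 0.30 × 0.40 × 0.5821 = 0.070. Letting c run over 30-50% and p over 10-50%, the gain runs from 0.10 × 0.30 × 0.5437 = 1.6 points to 0.50 × 0.50 × 0.5821 = 14.6 points.

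**Second model.** Suppose a fraction p × c of responders never relapses and the rest have a 6-month median. With p = 10-50% and c = 30-50%, the observed median becomes 6.3 to 9.5 months, and mean remission time restricted to 36 months goes from 8.5 to between 9.3 and 15.4 months.

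**The case against.** - **Other treatment is barred.** Section 5.2 says that "throughout this study, subjects may not receive any other chemotherapy or any investigational agent", and concomitant anti-cancer treatment is on its exclusion list. This does not settle the matter. Transplant is not named, it is unclear whether the bar reaches into long-term follow-up, and the 28-day rules in Sections 5.2 and 8.2 themselves expect new anti-cancer therapy. A bar also gives the analyst no rule for a subject who receives such therapy.
- **The data may exist anyway.** A reader might infer that the date of transplant can never be recovered. The documents do not support that. The quoted sentence ends the record of concomitant medications but does not forbid noting the therapy that triggers it. Staff must know of that therapy to apply the rule, the case report form is not in the documents, and Section 13.6 retains hospital records. Retrospective abstraction is possible. It is neither planned nor assured.
- **OS.** A reader might also infer that OS is inflated by rescue treatment and needs correcting. OS that includes later therapy is the ordinary treatment-policy estimand. Moreover, follow-up as written ends at progression, so survival gained after progression would be unobserved rather than counted.
- **Few may be transplanted.** The sentence in Section 1.1 goes on to say that most patients are not transplant candidates, citing failed salvage, comorbidity and lack of a donor. Two of the three eligibility routes require unsuitability for intensive or standard induction chemotherapy. This stands, and it is why the 10% column matters.
- **Censoring is not neutral.** Subjects chosen for transplant differ in prognosis, so censoring at transplant may be informative. Counting remission through transplant is a legitimate estimand if stated. This also stands: the need is for a stated strategy and the data to carry it out.
- **Limited reach.** These are unpowered, descriptive endpoints in a small single-arm trial, and Section 11.3.2 lacks time-to-event methods altogether. That limits the weight of the point without answering it.

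**Conclusion.** The point holds for response duration, and for PFS when transplant or other anti-leukemia therapy starts before progression. Therapy begun after progression affects neither. The recording rule, the visit schedule and the analysis section together leave out both the data item and the rule needed to interpret these endpoints.

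The size is uncertain because the transplant rate is unknown. Under the assumed model, the shift in 12-month remission is about 2 points at a 10% rate and about 7 to 12 points at 30-50%. The medians, the transplant rates and the 2-month timing are assumptions; only the 30-50% cure range comes from the protocol. A large overstatement is therefore possible but not shown.

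For OS, the defect is that follow-up stops at progression in the Synopsis, Table 1 (footnote 13) and Section 6.4, which does not fit an OS objective. The primary endpoint and its design are sound on this point. The change is worth making because it is cheap.

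**What to change.** 1. In Table 1 (long-term follow-up) and Section 6.4, record at the monthly contact the date and type of first subsequent anti-leukemia therapy, including transplant. Exempt this one item from the cut-off in Section 5.2.
2. In Section 11.3.2, report response duration and PFS twice: without censoring for subsequent therapy, and censored at its start. Note that the censoring may be informative.
3. Report OS without censoring for later therapy (treatment policy), and describe the number and timing of transplants.
4. Reconcile the OS objective with the rule in the Synopsis, Table 1 (footnote 13) and Section 6.4 that ends follow-up at progression.

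Items 1 to 3 cost one case report form entry at a contact that already takes place and one more descriptive analysis. The censored versions will show shorter durations and fewer events. If item 4 is resolved by following survival beyond progression, those monthly contacts would continue for progressed subjects. Sample size, type I error and power do not change: 24 evaluable and 30 enrolled.

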6. STUDY PROCEDURES

Please refer to the Study Events Schedule ([Table 1](#)).

6.1 Screening Procedures

Written informed consent must be obtained prior to performing any study-specific evaluations or tests. Tests or evaluations performed as standard of care within the specified screening period, but prior to informed consent, may be accepted for this study and need not be repeated.

The following screening assessments are required within 21 days prior to Cycle 1 Day 1 (C1D1), unless otherwise specified:

- Demographic data, including date of birth, gender, race, and smoking status (smoker or nonsmoker);
- Medical history, including major diseases and/or surgeries;
- Baseline signs and symptoms;
- Document all medications taken during the 3 weeks prior to screening;
- Physical examination;
- Weight;
- Bone marrow aspirate and/or biopsy for clinical classification, flow cytometry, cytogenetic classification, and identification of commonly tested mutations in AML, (within 42 days of start of treatment (C1D1));
- ECOG performance status (see Appendix B: ECOG Performance Status);
- 12-lead electrocardiogram (ECG), including rhythm, heart rate, and PR, QRS, and QTc intervals;
- Vital signs, including systolic and diastolic blood pressure, pulse rate, respiratory rate, and temperature;
- Hematology laboratory evaluations:
 - Complete blood count (CBC) including hemoglobin, hematocrit, white blood cell (WBC) absolute differential including circulating blasts, and platelet count;
- Blood chemistry laboratory evaluations:
 - BUN, creatinine, uric acid, total bilirubin, AST, ALT, alkaline phosphatase, LDH, sodium, potassium, calcium, magnesium, phosphorous, bicarbonate, chloride, glucose, albumin, and total protein;
- Serum pregnancy test within 7 days of Cycle 1 Day 1 for females of childbearing potential; and
- Adverse event (AE) assessment (starting when the subject provides written informed consent).

6.2 On-Study Evaluations

Cycle 1 Day 1

All subjects will have the following procedures completed on the Cycle 1 Day 1 visit, unless otherwise specified:

- Document concomitant medications and transfusions;
- AE assessment;
- Physical exam;
- Vital signs, including blood pressure, pulse, respirations, and temperature;
- Weight;
- ECOG Performance Score;
- Hematology laboratory evaluations (unless performed in the 24 hours prior to visit):
 - Complete blood count (CBC) including hemoglobin, hematocrit, white blood cell (WBC) absolute differential including circulating blasts, and platelet count; and
- Blood chemistry laboratory evaluations (unless performed in the 24 hours prior to visit):
 - BUN, creatinine, uric acid, total bilirubin, AST, ALT, alkaline phosphatase, LDH, sodium, potassium, calcium, magnesium, phosphorous, bicarbonate, chloride, glucose, albumin, and total protein.

Cycle 1 Day 8

All subjects will have the following procedures:

- Document concomitant medications and transfusions;
- AE assessment;
- Physical exam;
- 12-lead electrocardiogram (ECG), including rhythm, heart rate, and PR, QRS, and QTc intervals;
- Vital signs, including blood pressure, pulse, respirations, and temperature;
- Weight;
- ECOG Performance Score;
- Hematology laboratory evaluations (unless performed in the 24 hours prior to visit):
 - Complete blood count (CBC) including hemoglobin, hematocrit, white blood cell (WBC) absolute differential including circulating blasts and platelet count;
- Blood chemistry laboratory evaluations (unless performed in the 24 hours prior to visit):
 - BUN, creatinine, uric acid, total bilirubin, AST, ALT, alkaline phosphatase, LDH, sodium, potassium, calcium, magnesium, phosphorous, bicarbonate, chloride, glucose, albumin, and total protein; and

Cycle 1 Days 15 and 22

All subjects will have the following procedures:

- Document concomitant medications and transfusions;
- AE assessment;
- Physical exam;
- Vital signs, including blood pressure, pulse, respirations, and temperature;
- Weight;
- ECOG Performance Score;

- Hematology laboratory evaluations (unless performed in the 24 hours prior to visit):
 - Complete blood count (CBC) including hemoglobin, hematocrit, white blood cell (WBC) absolute differential including circulating blasts and platelet count; and
- Blood chemistry laboratory evaluations (unless performed in the 24 hours prior to visit):
 - BUN, creatinine, uric acid, total bilirubin, AST, ALT, alkaline phosphatase, LDH, sodium, potassium, calcium, magnesium, phosphorous, bicarbonate, chloride, glucose, albumin, and total protein.

Cycle 1 Day 28

The C1D28 visit may occur \pm 48 hours from the protocol-specified date. All subjects will have the following procedures:

- Document concomitant medications and transfusions;
- AE assessment;
- Physical exam;
- Vital signs, including blood pressure, pulse, respirations, and temperature;
- Weight;
- 12-lead electrocardiogram (ECG), including rhythm, heart rate, and PR, QRS, and QTc intervals;
- ECOG Performance Score;
- Hematology laboratory evaluations:
 - Complete blood count (CBC) including hemoglobin, hematocrit, white blood cell (WBC) absolute differential including circulating blasts, and platelet count;
- Blood chemistry laboratory evaluations:
 - BUN, creatinine, uric acid, total bilirubin, AST, ALT, alkaline phosphatase, LDH, sodium, potassium, calcium, magnesium, phosphorous, bicarbonate, chloride, glucose, albumin, and total protein;
- Bone marrow aspirate and/or biopsy for clinical classification (cellularity, blast assessment) and cytogenetic testing, ; and
- Serum or urine pregnancy test – if applicable for females of childbearing potential.

At C1 D28, the subject will have completed protocol-specified treatment for Cycle 1. For subjects in Phase Ib, DLT assessment will occur at this point.

Cycle 2/Days 1, 8, 15, and 22

All subjects will have the following procedures completed on the visit, unless otherwise specified:

- Document concomitant medications and transfusions;
- AE assessment;
- Physical exam;
- Vital signs, including blood pressure, pulse, respirations, and temperature;
- Weight;
- ECOG Performance Score;
- Hematology laboratory evaluations (unless performed in the 24 hours prior to visit):
 - Complete blood count (CBC) including hemoglobin, hematocrit, white blood cell (WBC) absolute differential including circulating blasts, and platelet count; and

- Blood chemistry laboratory evaluations (unless performed in the 24 hours prior to visit):
 - BUN, creatinine, uric acid, total bilirubin, AST, ALT, alkaline phosphatase, LDH, sodium, potassium, calcium, magnesium, phosphorous, bicarbonate, chloride, glucose, albumin, and total protein.

Cycle 2 /Day 28 (± 2) and EOT (± 7)

The Day 28 visit may occur ± 48 hours and EOT may occur within 7 days from the protocol-specified date. All subjects will have the following procedures:

- Document concomitant medications and transfusions;
- AE assessment;
- Physical exam;
- Vital signs, including blood pressure, pulse, respirations, and temperature;
- Weight;
- ECOG Performance Score;
- Hematology laboratory evaluations:
 - Complete blood count (CBC) including hemoglobin, hematocrit, white blood cell (WBC) absolute differential including circulating blasts, and platelet count;
- Blood chemistry laboratory evaluations:
 - BUN, creatinine, uric acid, total bilirubin, AST, ALT, alkaline phosphatase, LDH, sodium, potassium, calcium, magnesium, phosphorous, bicarbonate, chloride, glucose, albumin, and total protein;
- Bone marrow aspirate and/or biopsy for clinical classification (cellularity, blast assessment) and cytogenetic testing; and
- Serum or urine pregnancy test – if applicable for females of childbearing potential
- 12-lead electrocardiogram (ECG), including rhythm, heart rate, and PR, QRS, and QTc intervals (only at EOT)

If a subject achieves CR, or at end of treatment bone marrow assessments will be performed as clinically indicated.

